This is a prospective, multicenter, open-label, single-arm, Phase I/II trial of human retinal progenitor cells (jCell) for the treatment of retinitis pigmentosa (RP). Study subjects will be screened for eligibility, informed consent obtained, baseline studies of primary and exploratory endpoints performed. Then the subjects will be treated with one of two doses of jCell, with initially enrolled patients receiving the lower dose.

Cohort 1: BCVA no better than 20/200 and no worse than Hand Motions

The first four subjects in Cohort 1 will receive an intravitreal injection of 0.5×10^6 hRPC (50 µL volume) into the eye with the worst visual acuity; only one eye will be injected. Subjects will be monitored closely following injection for 60 minutes prior to being released home on the day of treatment, based on intraocular pressure <30mm Hg and vital signs returned to pre-injection. Patients will be treated with ophthalmic corticosteroid eye drops to minimize any inflammation from injection for up to 14 days (including tapering schedule). There will be a minimum four week interval between the treatment of the first and second subjects in this cohort to confirm no serious injection related AEs have occurred for subject #1 prior to treatment of subject #2. Subsequent cohort 1 subjects at the same dose level will be spaced at least one week apart (subjects 2, 3 and 4). All subjects will receive injection of cells into the eye with the poorest visual acuity. Following at least one week of safety observations for the last study subject at the lower dose level, safety and tolerability data will be reviewed by the DSMB.

Assuming no unexpected safety issues, an additional 4 subjects will be enrolled in Cohort 1 and treated at the second dose level, 1.0×10^6 hRPC. Treatment will be similar to the first four subjects, i.e. intravitreal injection under topical anesthesia with treatment of the first two subjects separated by at least 4 weeks and subsequent subjects in this cohort (subject 6, 7 and 8) spaced at least one week apart. Following at least one week of safety observation for the last Cohort 1 subject, safety and tolerability data will be reviewed by the DSMB prior to initiation of Cohort 2.

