Since this is an exploratory study, no formal hypothesis testing will be done. Descriptive statistics will be used to tabulate and summarize study outcomes. The baseline results of clinical examinations of the injected eye serve as controls for the injected eye. Results of testing of the non-tested eye will also be described. Continuous variables will be summarized descriptively (sample size, mean standard deviation and error, minimum and maximum). Discrete variables will be summarized by frequency or percentage, and analyzed with non-parametric statistics.

Safety:

The safety analyses of AEs and laboratory parameters will include descriptive statistics. Summaries of AEs will be generated by type (AE or SAE), body system and preferred term, severity, and relationship to study product.

TABLE OF CONTENTS

1.0	INT	RODUCTION1	10
1.1	BA	ckground	
1.	1.1	Retinitis Pigmentosa 10	
1.	1.2	Stem /Progenitor Cells	
1.	1.3	CNS and Retinal Progenitor Cells11	
1.2	JCE	ELL (HUMAN RETINAL PROGENITOR CELLS, HRPC)12	
1.3	RA	TIONALE FOR THE PROPOSED STUDY	
2.0	OBJ	ECTIVES 1	14
2.1	Pri	MARY OBJECTIVE	
2.2	SEC	CONDARY OBJECTIVES	
3.0	STU	DY DESIGN1	14
3.1	STU	JDY POPULATION	
3.	1.1	Cohort One	
3.	1.2	Cohort Two 16	
3.2	En	DPOINTS	
3.2	2.1	Efficacy Endpoints	
3.2	2.2	Safety Endpoints 17	
3.3	STU	JDY DURATION	
3.4	EA	rly Study Termination	
4.0	SUB	JECT SELECTION 1	18
4.1	Inc	CLUSION CRITERIA	
4.2	Exe	clusion Criteria	
4.3	Su	BJECT WITHDRAWAL CRITERIA	
4.4	Dis	SCONTINUATION/WITHDRAWAL PROCEDURES	
5.0	SUB	JECT REGISTRATION	20
6.0	TRE	ATMENT PLAN	21
6.1	Do	se and Schedule	
CONF	FIDEN	TIAL 7 of 41	

6.2		TREATMENT COMPLIANCE			
6.3		SUP	UPPORTIVE CARE/PROHIBITED TREATMENTS		
7.0	S	TUI	DY EVALUATIONS		
7.1		SCR	EENING		
7.2		Bas	ELINE (SHOULD BE WITHIN 30 DAYS OF TREATMENT)		
7.3		BEF	ORE ADMINISTRATION OF JCELL (DAY 0)	24	
7.4		Aft	FER ADMINISTRATION OF A SINGLE INTRAVITREAL DOSE OF JCELL (DAY ())24	
7.5		Fol	LOW UP VISITS	25	
7	.5.1		Day 1 (24 hours)	25	
7	.5.2	2	Day 2 (48 hours)		
7	.5.3	5	Day 7 (week one)	25	
7	.5.4	ļ	Day 14 (week two) +/- 1 day		
7	.5.5	5	Day 21 (week three) +/- 1 day		
7	.5.6)	Day 28 (week four/month 1) +/- 1 day		
7	.5.7	7	Month 2 (Day 60) +/- 4 days		
7	.5.8	8	Month 3 (Day 90) +/- 4 days		
7	.5.9)	Month 4 (Day 120) +/- 4 days		
7	.5.1	0	Month 5 (Day 150) +/- 4 days		
7	.5.1	1	Month 6 (Day 180) +/- 4 days		
7	.5.1	2	Month 9 (Day 270) +/- 4 days		
7.6		End	O OF TREATMENT (MONTH 12) OR EARLY TERMINATION VISIT		
8.0	A	SSE	ESSMENTS		
8.1		SAF	ETY ASSESSMENTS		

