3.2 Endpoints

3.2.1 Efficacy Endpoints

The response to jCell injection will be assessed based on the following:

- Change in BCVA at scheduled time points compared to baseline as well as contralateral eye. Acuity testing will be standardized using E-ETDRS.
- Changes in ellipsoid zone (EZ) band width at specified time points based on Spectral Domain Optical Coherence Tomography (OCT) compared to baseline as well as contralateral eye.
- Changes in electroretinogram (ERG) physiologic analysis compared to baseline as well as contralateral eye.
- Visual field sensitivity at scheduled time points post-treatment, using Goldmann visual field area and Humphrey 10-2, in subjects with adequate fixation to allow reliable testing.

In addition to the assessments listed above, a number of visual assessments that may be more appropriate for low vision subjects have been recommended by low vision experts. While BCVA is the gold standard for vision assessment, it is clear that this test is not particularly CONFIDENTIAL 16 of 41

relevant or accurate for subjects with very poor vision (legally blind). As there is little experience with our treatment approach, and subjects with very advanced vision loss are included in Cohort 1, it is planned to try some non-invasive assessments in subgroups of subjects, dependent upon the subjects' visual range and capabilities. These assessments include but are not limited to trial frame refraction, testing for contrast sensitivity (examples include Pelli-Robson Contrast Sensitivity Chart, Mars Letter Contrast Sensitivity Test, low luminance testing and mixed contrast eye charts); testing for color vision changes (e.g. D15 large caps, pseudoisochromatic plates), FrACT, California Central Visual Field Test, Tangent Screen Perimetry, ADL questionnaire (e.g. VFQ25, activity inventory, Low Vision Visual Functional Questionnaire [LF-VFQ], Function Independence Measures [FIM], Prosthetic Low Vision Rehabilitation [PVoVR]) and testing for changes in reading ability (e.g. Continuous Text Reading, MN Read). The goal of exploring some or all of these assessments is to develop a qualified, quantitative tool or set of tools for assessing post-treatment changes.

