9. METHODS OF EFFICACY ANALYSIS

Since this is an exploratory study, no formal hypothesis testing will be done. Descriptive statistics will be used to tabulate and summarize study outcomes. The baseline results of clinical examinations of the non-injected (non-study) eye serve as controls for the injected (study) eye. Results of clinical testing of the non-injected eye will also be described. Continuous variables will be summarized descriptively (sample size, mean, standard deviation and error, minimum and maximum). Discrete variables will be summarized by frequency or percentage. All efficacy analyses will be based on the ITT Population. All efficacy variables will be presented by cohort and dose level using summary statistics.

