Programmer Note: Table 14.2.1.4 will contain the same information for the Non-Study Eye Programmer Note: Denominators used for percentage calculation to be based on number of results reported for that perticular time point.

Table 14.2.1.5 Best Corrected Visual Acuity (ETDRS): Study Eye vs Non-Study Eye Number of Letters correct ITT Population

	0.5 x	10 ⁶ hRPC	1.0 x	10 ⁶ hRPC	2.0 x	10 ⁶ hRPC	3.0x	10 ⁶ hRPC
	Study Eye (N=)	Non-Study Eye (N=)						
Baseline ^[1]								
n	n	n	n	n	n	n	n	n
Mean (SD)	xx.x (xx.x)	xx.x (xx.x)						
Median	xx.x	XX.X	xx.x	xx.x	xx.x	XX.X	xx.x	xx.x
Min, Max	xx, xx	XX, XX						
Month 3								
n	n	n	n	n	n	n	n	n
Mean (SD)	xx.x (xx.x)	xx.x (xx.x)						
Median	XX.X	XX.X	xx.x	XX.X	XX.X	XX.X	xx.x	XX.X
Min, Max	xx, xx	XX, XX						
Month 3 Change from Baseline								
n	n	n	n	n	n	n	n	n
Mean (SD)	xx.x (xx.x)	xx.x (xx.x)						
Median	xx.x	xx.x	xx.x	xx.x	xx.x	xx.x	xx.x	xx.x
Min, Max	xx, xx	XX, XX						
Difference between Study Eye Vs Non- Study Eye								
n		n		n		n		n
Mean (SD)		xx.x (xx.x)		xx.x (xx.x)		xx.x (xx.x)		xx.x (xx.x)
Median		XX.X		XX.X		XX.X		XX.X
Min, Max		xx, xx		xx, xx		xx, xx		XX, XX

^[1] Baseline is defined as the value obtained at the baseline visit. If the baseline value is missing, the baseline value will be the last non-missing value recorded prior to the first dose of study drug. path/t_program.sas date time

Programmer Note: Continue table for Visits: Month 3, Month 6, Month 9, Month 12 or Early Term.

jCyte, Inc. Protocol: JC-01

Table 14.2.1.6 Categorical Analysis of Best Corrected Visual Acuity (ETDRS): Study Eye vs Non-Study Eye Number of Letters correct ITT Population

	0.5 x 1	0 ⁶ hRPC	1.0 x 1	0 ⁶ hRPC	2.0 x 10	⁰ hRPC	3.0 x 10	0 ⁶ hRPC
	Study Eye (N=)	Non-Study Eye (N=)						
Proportion of Subjects with Specified increase in letters correct for any Post Baseline Assessment	(n=)	(n=)	(n=)	(n=)	(n=)	(n=)	(n=)	(n=)
>=5 Letters Increase	n (%)	n (%)						
>=10 Letters Increase	n (%)	n (%)						
>=15 Letters Increase	n (%)	n (%)						
Proportion of Subjects with Specified increase in letters correct at Month 3	(n=)	(n=)	(n=)	(n=)	(n=)	(n=)	(n=)	(n=)
>=5 Letters Increase	n (%)	n (%)						
>=10 Letters Increase	n (%)	n (%)						
>=15 Letters Increase	n (%)	n (%)						
Proportion of Subjects with Specified increase in letters correct at Month 6	(n=)	(n=)	(n=)	(n=)	(n=)	(n=)	(n=)	(n=)
>=5 Letters Increase	n (%)	n (%)						
>=10 Letters Increase	n (%)	n (%)						
>=15 Letters Increase	n (%)	n (%)						

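### The planned letter-gain responder tables do not pair the two eyes, and the standard error the plan states is printed in no BCVA table

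*Protocol*

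**What the plan says.** The protocol describes a "prospective, multicenter, open-label, single-arm, Phase I/II trial". Section 3.2.1 lists as an efficacy endpoint "Change in BCVA at scheduled time points compared to baseline as well as contralateral eye".

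The synopsis and section 10.2 rule out formal hypothesis testing. In the same paragraph they say "Continuous variables will be summarized descriptively (sample size, mean standard deviation and error, minimum and maximum" and "Discrete variables will be summarized by frequency or percentage, and analyzed with non-parametric statistics". No non-parametric method is named.

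SAP section 9 keeps the standard error for continuous variables but shortens the other sentence to "Discrete variables will be summarized by frequency or percentage", without explanation. SAP section 5 lists mean, SD, median, minimum and maximum, with no standard error. The decimal rules in Appendix A do not mention one either.

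In the SAP Appendix C shells:
- Tables 14.2.1.1, 14.2.1.2 and 14.2.1.5 (letters correct) show n, mean (SD), median, minimum and maximum.
- Table 14.2.1.5 also has a between-eye difference block for each dose level, with the same statistics.
- Tables 14.2.1.3 and 14.2.1.4 put study-eye and fellow-eye responders in separate tables.
- Table 14.2.1.6, titled "Categorical Analysis of Best Corrected Visual Acuity (ETDRS): Study Eye vs Non-Study Eye", prints one n (%) per eye for each dose level. Its denominators are the results reported at each time point.

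The documents also differ on which measurements act as control. The protocol says "The baseline results of clinical examinations of the injected eye serve as controls for the injected eye". SAP section 9 says "The baseline results of clinical examinations of the non-injected (non-study) eye serve as controls for the injected (study) eye".

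**The concern.** Each subject contributes both eyes, so the two responder percentages are paired. Gains in both eyes of a subject point towards learning, effort or test variability. Gains in the study eye alone are what a local effect would produce, although other explanations remain. The two percentages cannot separate these patterns. The precision of their difference depends on how many subjects are discordant, and no planned table reports that number. Because the denominators follow the results reported for each eye, the two percentages may not even describe the same subjects at a visit.

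For mean change the planned difference is adequate in substance. However, the standard error stated in protocol 10.2 and SAP section 9 appears in no BCVA shell, so the SAP disagrees with itself. At stake is how well a reader can judge the only concurrent efficacy comparison in the trial.

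**Working it through.** **Planned numbers.** Each vision cohort has 4 + 4 + 3 + 3 subjects over four dose levels, and 2 × 14 = 28 reproduces the stated maximum. With cohorts combined, as in Tables 14.2.1.5 and 14.2.1.6, the dose groups have 8, 8, 6 and 6 subjects. The documents give no alpha, power, effect size or SD for BCVA change.

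**Responders.** Let b be the subjects who gain in the study eye only and c those who gain in the fellow eye only. The paired difference is (b − c)/n, with

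SE = √[(b + c) − (b − c)²/n] / n.

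The two percentages fix b − c but not b + c. The responder counts below are assumptions chosen for illustration. Both examples give a difference of 25 points.

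| Assumed counts | Overlap between eyes | b, c | SE |
|---|---|---|---|
| 14/28 v 7/28 | maximal: 7 gain in both | 7, 0 | √(7 − 1.75)/28 = 0.082 |
| | independence: 14 × 7/28 = 3.5 expected in both | 10.5, 3.5 | √(14 − 1.75)/28 = 0.125 |
| | none gain in both | 14, 7 | √(21 − 1.75)/28 = 0.157 |
| 4/8 v 2/8 | maximal: 2 gain in both | 2, 0 | √(2 − 0.5)/8 = 0.153 |
| | independence: 4 × 2/8 = 1 in both | 3, 1 | √(4 − 0.5)/8 = 0.234 |
| | none gain in both | 4, 2 | √(6 − 0.5)/8 = 0.293 |

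Counts out of 28 would have to be read from the total columns of Tables 14.2.1.3 and 14.2.1.4, because Table 14.2.1.6 has no total column. In every row the printed percentages would be the same.

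**Mean change.** Table 14.2.1.5 supplies n and the SD of the between-eye difference. The SAP 9.1 text does not say that the difference is taken within subject, but an SD, median and range in that block imply it. Then SE = SD/√n, and the 95% half-width is t(0.975, n − 1) × SD/√n:
- n = 8: 0.84 SD
- n = 6: 1.05 SD

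For an assumed SD of 5 to 15 letters, that is 4.2 to 12.5 letters at n = 8 and 5.2 to 15.7 letters at n = 6.

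**The case against.** The strongest reply is that the main between-eye comparison is already paired. The difference block in Table 14.2.1.5 nets out gains shared by both eyes and uses the letter score without dichotomising it. Listing 16.2.6.1 shows both eyes by subject and visit, so in groups of 6 or 8 the discordant subjects can be counted by hand. Efficacy is exploratory, the sample size has no statistical basis, and no decision rule uses the responder tables. The non-parametric clause names no method and sits awkwardly beside the statement that nothing will be tested, so dropping it may be deliberate.

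Much of this stands. It makes the responder gap one of reporting, with no data lost, and it limits the severity. It does not justify leaving readers to rebuild a table whose title sets one eye against the other. Nor does it explain why a standard error stated in SAP section 9 is absent from SAP section 5 and the shells.

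Two limits on the illustration also stand. The responder counts are invented. The largest standard errors require that no subject gains in both eyes, a negative association that runs against shared learning or effort. With non-negative association the ranges are 8.2 to 12.5 points for 28 subjects and 15 to 23 points for 8.

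**Conclusion.** For responders, neither the number gaining in the study eye only nor the precision of the paired difference can be derived from any planned table. Under the assumed counts the standard error could differ by a factor of about 1.5 (8.2 v 12.5 points, or 15.3 v 23.4) without any change in what is printed, and by more if no subject gains in both eyes. For mean BCVA change the standard error can be derived but is not printed.

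Three stronger readings are tempting and are not supported:
- A reader might infer that no planned table conveys the precision of the eye-to-eye comparison. Table 14.2.1.5 gives n and SD of the difference, which is enough to compute it.
- A reader might take study-eye-only gains as evidence of treatment effect. The protocol treats the eye with poorer acuity and the trial is open-label, so regression to the mean, unequal room to improve and expectation could all produce them. Pairing addresses sampling error only.
- A reader might set the half-widths above against the 10-letter change in protocol 8.2.1. That figure concerns an individual's change from baseline, not a group mean, so the two are not comparable.

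This is a modest improvement to exploratory efficacy reporting. The primary safety objective is unaffected.

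**What to change.** 1. In Table 14.2.1.6, for each threshold and visit and among subjects with both eyes measured, add counts for gain in the study eye only, fellow eye only, both and neither. Add the paired difference in proportions with a 95% interval suited to small n (exact or score type, not Wald).
2. In the between-eye difference block of Table 14.2.1.5, add the standard error and a t-based 95% interval. Align SAP section 5 and the other continuous BCVA shells with SAP section 9.
3. Replace the unspecified non-parametric analysis in the protocol synopsis and section 10.2 with this descriptive paired summary, or state in the SAP that it is withdrawn. Report no p-values.
4. State in the SAP that the intervals describe sampling error only and do not remove bias from treating the worse eye or from open-label testing. While revising section 9, reconcile its description of the control with the protocol's.

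The cost is some SAP wording and a few rows in the BCVA shells. No new data are needed: letters missed for each eye are in Listing 16.2.6.1 and the study eye is in Listing 16.2.4.1. The downside is that wide intervals will make the results look less favourable.

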1.0 INTRODUCTION

1.1 Background

1.1.1 Retinitis Pigmentosa

Retinitis pigmentosa (RP) refers to a group of inherited diseases causing retinal degeneration. The cell-rich retina lines the back inside wall of the eye. It is responsible for capturing images from the environment. People with RP experience a gradual decline in their vision because photoreceptor cells (rods and cones) die. Forms of RP and related diseases include Usher syndrome, Leber's congenital amaurosis, rod-cone degeneration, Bardet-Biedl syndrome, and Refsum disease, among others.

In most forms of RP, rods are affected first. Because rods are concentrated in the outer portions of the retina and are triggered by dim light, their degeneration affects peripheral and night vision. When the more centrally located cones - responsible for color and sharp central vision - become involved, the loss is in color perception and central vision. Night blindness is one of the earliest and most frequent symptoms of RP.

RP is typically diagnosed in adolescents and young adults. The classic clinical sign of the disease is the presence of dark deposits in the retina. The main risk factor is a family history of retinitis pigmentosa. It is an uncommon condition affecting about 1 in 4,000 people or roughly 100,000 individuals in the US¹. Cases of RP are associated with a wide variety of known gene mutations, with new mutations still being discovered. The mutations can be inherited from one or both parents, or occur spontaneously; the pattern of inheritance can be autosomal recessive, autosomal dominant, X-linked or mitochondrial.

There is no effective treatment for RP; once photoreceptors are lost, they do not regenerate. The rate of deterioration of vision varies from person to person, with most people with RP legally blind by age 40. People with RP also often develop cataracts at an early age, or swelling of the retina (retinal edema). Numerous breakthroughs in the treatment of cataract and corneal disease have greatly decreased the incidence of blindness from these causes. In contrast, treatment of retinal and optic nerve disease is more limited, with these conditions now representing major causes of incurable visual loss and a significant unmet medical need.

1.1.2 Stem /Progenitor Cells

No restorative treatments for retinal cell loss currently exist, but stem cell treatment has emerged as a particularly promising strategy. In addition, the concept of delaying retinal cell death through the use of neuroprotective agents has considerable merit and committed progenitor cells are useful platforms for delivery of neuroprotective cytokines. Also, the possibility of reinvigorating nonfunctional yet viable cones is an underappreciated yet attractive potential clinical target.

Cells and tissues of many types survive injection to the subretinal space, in part because this location exhibits characteristics often referred to as those of an "immune privileged" site². Both photoreceptors³ and RPE cells^{4,5} survive beneath the retina, however, failure of donor photoreceptors to integrate with surviving host circuitry and failure of donor RPE cells to adhere to Bruch's membrane have thus far frustrated attempts to achieve functional repair using these methods. For photoreceptors, there is a fundamental problem that must be overcome, namely the physical barrier to neurite outgrowth posed by the outer limiting membrane (OLM). In photoreceptor degeneration, the OLM undergoes hypertrophy and regenerating neurites are impeded by this barrier⁶. Glial hypertrophy has been often been implicated in the failure of endogenous regenerative mechanisms to bridge a lesion⁷, e.g., after spinal cord injury⁸.

1.1.3 CNS and Retinal Progenitor Cells

It has been demonstrated that transplanted CNS progenitor cells are not impeded by the hypertrophied OLM and cross in large numbers^{9,10}. The ability to migrate into the mature retina is characteristic of CNS progenitor cells, which do not simply migrate, but exhibit widespread integration into the local cytoarchitecture, with pronounced tropism for areas of disease.

Hippocampal progenitors transplanted to the vitreous of neonatal rats integrated into the retina and developed morphologies appropriate to their layer of residence¹¹. In the dystrophic Royal College of Surgeons (RCS) rat, it has been shown that grafted hippocampal progenitors developed rod photoreceptor-like morphologies and extended neurites into the optic nerve⁹; however, brain-derived progenitors did not express retina-specific markers. This lineage restriction has been overcome using progenitor cells derived from the retina. Retinal progenitor cells can be derived from the developing neural retina of rats, mice, pigs, cats and humans.

The first simultaneous sourcing of retinal- and brain-derived neural progenitors from the same premature infant occurred in 1999 and both progenitor cell types were found to express MHC I antigens, but not MHC II¹². Cultured hRPCs expressed a range of markers consistent with CNS progenitor cells. hRPCs could be distinguished from human brain progenitor cells by the expression of retinal specification genes, particularly recoverin. More recently, age 18 weeks gestation was found to be a suitable age developmental stage for isolation of hRPCs.

Although rejection is the norm for grafts between individuals of disparate genetic background, this tendency is markedly less problematic when placed in an "immune privileged" site such as the eye. This does not mean that allogeneic grafts to these sites cannot be rejected, but that they benefit from a decreased likelihood of rejection. It has also been shown that CNS progenitor cells themselves exhibit properties of cell-specific immune privilege. Rat hippocampal progenitor cells were not recognized by human mononuclear cells in vitro¹³ and murine brain progenitor cells survived transplantation to the allogeneic kidney CONFIDENTIAL 11 of 41 capsule, a non-privileged site¹⁴. The mechanisms underlying cell-specific immune privilege may relate in part to the major histocompatibility (MHC) antigens.

Studies have indicated that MHC class I expression is consistent for progenitors from different individuals or strains within a given species. This is the case for multiple examples of CNS progenitors from the brain and retina of mouse and human. Another trend, of considerable importance to clinical transplantation studies, is an absence of detectible MHC class II expression for all CNS progenitor cells examined from mouse, rat, and human. The classical mechanism of graft rejection involves the nonspecific recognition of foreign MHC class II molecules by CD4+ host lymphocytes. Hence, an absence of class II molecules would allow grafted progenitor cells to evade immune rejection mediated by this important mechanism. CNS progenitor cells therefore differ from solid tissue grafts of either brain or retina, both of which contain class II-expressing cells.

1.2 jCell (human Retinal Progenitor Cells, hRPC)

The investigational product (jCell) to be tested is a live suspension of $0.5-1.0 \times 10^6$ human retinal progenitor cells (hRPC) suspended in clinical grade medium. The hRPC are of allogeneic human fetal origin. Following manufacture, the hRPC intended for therapeutic use are cryopreserved using 90% complete growth medium and 10% DMSO in a controlled-rate freezer. The characteristics and functional properties of the investigational product are summarized in the following table (Table 1). Most functional assays are performed after the cryopreserved cells are thawed and cultured for 24-48 hours, as is planned for the initial clinical study.

Test	Results
Cell count and viability	$1.0 - 1.6 \ge 10^{6}$ /mL with at least 85% viability post-thaw
Protein expression by immunocytochemistry	jCell is positive for the expression of Nestin (a marker of neural stem cells), Sox2 (a transcription factor essential for self-renewal) and Ki67, a marker of proliferation
Gene expression by qPCR	jCell is positive for the expression of Nestin and Sox2; jCell is negative for the expression of RHO (rhodopsin gene) and the pluripotency marker, Nanog
MHC markers profile by flow cytometry (FACS)	MHC Class I antigens are expressed on >75% of cells and MHC Class II antigens on <2% of cells in the product
Neurogenesis	Cells in product differentiate into retinal neuronal or glial cell types in culture based on expression of genes associated with different retinal neuronal/glial cell types

Test	Results
	as assessed by qPCR.
OPN gene and protein expression by qPCR and ELISA, respectively	Cells are positive for gene and protein expression of OPN with >40 ng per million cells over a 24 hour period
Karyotype	Cells have a normal human karyotype
In vitro tumorigenicity	jCell is unable to form colonies in a standard soft agar colony formation assay.
Human telomerase reverse transcriptase (hTERT)gene expression by qPCR	Cells are negative for expression of the hTERT gene.

A range of non-clinical studies has been performed to assess the functionality and distribution of injected hRPC. Collectively the nonclinical data have demonstrated that allogeneic grafts show prolonged survival in the vitreous, retina, and subretinal space in all mammalian species tested, despite the absence of immunosuppressive agents, with evidence of graft-associated benefits at the behavioral level, specifically with respect to neuroprotection of host photoreceptors. Prolonged survival is possible except in cases of xenotransplantation to non-immunosuppressed animals, and differentiation with expression of relevant markers together with functional rescue has been demonstrated in animal models. The scope, duration, and exposure achieved in these studies are considered to be fully supportive of the planned human clinical trials.

